9. RESEARCH METHODS

9.1. Study design

This is a UK, multi-centre, retrospective, non-interventional cohort study based on secondary use of hospital medical records (paper-based and/or electronic, as appropriate). Three to five out of the 31 NHS Trusts that treated the largest number of patients with InO as part of the CUP will be initially selected for this study (the number of centres may be further expanded). A retrospective design has been selected as data have already been recorded into medical records and are available for data collection. The study is non-interventional as all patients received InO as part of routine clinical care, either *via* enrolment into the CUP or *via* private purchase.

Endpoints related to the primary objective are as follows and will be further described in Section 7.3:

- Summary measures of demographic characteristics (age and sex)
- Summary measures of clinical characteristics, including date of disease, stage of disease , C22-positive/negative, ALL cytogenetics, and Eastern Cooperative Oncology Group (ECOG) performance status, number of relapses prior to InO initiation.
- Summary measures of ALL-related treatments prior to InO initiation, and response to treatment.
- Baseline laboratory measurement including: blood indicators (full blood counts, platelets and absolute neutrophil counts [ANC]), liver function tests alanine aminotransferase (ALT), aspartate aminotransferase (AST), alkaline phosphatase (ALP), bilirubin, albumin and gamma glutamyl transferase (GGT).

Endpoints related to the secondary objective are as follows and will be further described in Section 7.3:

- Summary measures of InO treatment including: duration, number of cycles per patient, dose at initiation, dose modifications and discontinuation status (including reasons).
- Summary measures of azole antifungal therapy concomitant to InO treatment.
- Summary measures of CR, CRi and CR/CRi rates at end of InO cycles of treatment; overall and according to the number of salvage therapies in the pre-index observation period (0, 1, ≥ 2).
- Summary measures of MRD negativity at the end of InO cycles of treatment; and the number and proportion of patients attaining MRD negativity overall and according to the number of completed cycles of InO at the time of attainment (after 1, 2, ≥ 3 cycles of InO).
- The number and proportion of patients surviving at 3, 6 and 12 months after InO initiation, and cause of death; overall and in patients with and without HSCT.

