- Median OS (95% CI); overall and in patients with and without HSCT.
- The number and proportion of patients who are relapse-free at 3, 6 and 12 months after InO initiation; overall and in patients with and without HSCT.
- Median RFS (95% CI); overall and in patients with and without HSCT.
- Median NRM (95% CI) in patients undergoing follow-up HSCT from the date of HSCT.
- Number and proportion of patients undergoing follow-up HSCT, initiating chimeric antigen receptor (CAR) -T cell therapy, and initiating chemotherapy regimens after InO treatment.
- Number and proportion of patients experiencing documented diagnoses of VOD/SOS during the post-index observation period, overall, by grade and in the subset of patients (1) post-chemotherapy and (2) post-HSCT; treatment received for VOD/SOS including defibrotide and heparin.
- Number and proportion of patients experiencing grade 3/4 TRAEs (lung / cardiac / kidney) following InO initiation. Name of grade 3/4 TRAEs (lung / cardiac / kidney), name of treatment received, dose reduction / discontinuation of InO following TRAEs
- Number and proportion of patients experiencing other liver dysfunction following InO initiation. Name of liver dysfunction, name of treatment received, dose reduction / discontinuation of InO following TRAEs.

- CCI
[REDACTED]
[REDACTED]
[REDACTED]
[REDACTED]
[REDACTED]
[REDACTED]

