9.2. Setting

[figure not shown]
Key definitions

- Index date: the date of initiation of the first cycle of InO.
- Baseline period: period from 6 months prior to index date to index date. The closest observation recorded during the baseline period and closest to index date will be used as baseline data (when more than one observations are available).
- Pre-index observation period: period from the date of ALL diagnosis to the index date.
- Post-index observation period: period from the index date until the date of death, or date of latest visit at the time of data collection, whichever is soonest.
- CR/CRI rate: number of patients who achieve CR/CRI divided by the total number of patients completing treatment with InO (defined as patients with a recorded date of discontinuation of InO).

- MRD negativity rate: proportion of patients in whom MRD-negative status is observed, among patients in whom MRD negativity status has been assessed, at any time until the end of treatment with InO (defined as the date of recorded discontinuation of InO).
- OS: time from index date to death.
- RFS: time from index date to the earliest date of the following events: death, progressive disease (including objective progression, relapse from CR/CRi, treatment discontinuation due to global deterioration of health status), and start of new induction therapy or post-therapy HSCT without achieving CR/CRi.
- NRM: Time from the date of follow-up HSCT until death without disease progression

Patients will be observed from the start of the pre-index observation period until the end of the post-index observation period. For the purpose of identifying risk factors for VOD/SOS and replicating the findings by Kantarjian et al.⁷, follow-up will be defined as the post-index observation period, and patients will be censored at the date of the last recorded clinic visit prior to data collection.

Figure 1: Study design and observation periods

Three to five of the 31 NHS Trusts participating in the CUP that treated the largest number of patients with InO as part of the CUP (total number of patients including private purchase to be confirmed) will initially be selected for this study to achieve a target sample size of approximately 25 patients (the number of sites may be expanded at a later date). The list of selected sites will be maintained in a stand-alone document. Sites will be selected on the basis that:

- Their cancer service participated in the CUP.

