9.2.1. Inclusion criteria

The source population for this study is adult patients treated with InO at the selected sites and who accessed InO *via* NHS commissioning, *via* the CUP or *via* private purchase between June 2016 and February 2019. The NICE recommendation is as an option for treating relapsed or refractory CD22- positive B-cell precursor ALL in adults; and patients with relapsed or refractory Philadelphia chromosome positive disease should have had at least 1 tyrosine kinase inhibitor⁹ (see **Annex 1** for NICE eligibility criteria). The eligibility criteria for inclusion in the CUP are provided in Annex 1.

Patients will be eligible for inclusion in the present study if they fulfill all of the following criteria:

Inclusion criteria

- Patients with relapsed/refractory ALL.
- Patients who initiated InO between 1st of June 2016 and date of data collection.
- Patients who accessed InO treatment *via* NHS commissioning, via the CUP, or via private purchase.
- Patient aged ≥ 18 years old at initiation of InO treatment

Exclusion criteria

- Patients initiated on treatment with InO at a different hospital than the ones selected in this study.
- Patients with <3 months of follow-up since index date, unless death occurs <3 months from index date.

Eligible patients will be selected by chronological order and with a priority given to patients treated *via* NHS commissioning, if possible.

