
Secondary objective: To describe OS, and cause of death; in all patients and in patient with or without follow-up HSCT.
	

Summary measures of, in all patients, and separately in patients with and without follow-up HSCT:
 
 • The number and proportion of patients surviving at 3, 6 and 12 months after InO initiation • Cause of death • Median OS (95% CI) 	
Dates are DD/MM/YYYY unless specified
 
 • Date of InO initiation • Patient with follow-up HSCT: Yes/No • Patient alive at data collection (Y/N) • For deceased patients: date and cause of death leukaemia or TRM • For surviving patients: date of last visit before data collection

Secondary objective: To describe RFS in all patients and in patients with or without follow-up HSCT. Additionally, to describe NRM in patients undergoing follow-up HSCT.
	

Summary measures of, in all patients, and separately in patients with and without follow-up HSCT:
 
 • The number and proportion of patients who are relapse-free at 3, 6 and 12 months after InO initiation • Median RFS (95% CI) 
In patients undergoing follow-up HSCT:
	
Dates are DD/MM/YYYY unless specified
 
 • Date of InO initiation • Patient with follow-up HSCT: Yes/No • Patient alive at data collection (Y/N) • For deceased patients: date and cause of death • For surviving patients: date of last visit before data collection.

INOTUZUMAB
X9001222 NON-INTERVENTIONAL STUDY PROTOCOL
V1.0, 18 July 2019

 Median NRM (95% CI) from the date of follow-up HSCT 	
 Dates of the following events: death, progressive disease (including objective progression, relapse from CR/CRI, treatment discontinuation due to global deterioration of health status), and start of new induction therapy or post-therapy HSCT without achieving CR/CRI; as documented in medical records (if unavailable, infer using definitions above).

Secondary objective: To describe the treatments for ALL and responses to treatment post-InO, including HSCT, chemotherapy regimens and CAR T-cell therapy
	

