7.3. Subgroups

Where sample size allows ($n > 5$), the following endpoints will be analysed overall and separately for the subgroups stated below. The analyses will follow the methods described in [Section 10.1](#). More detail on the criteria for each subgroup can be found in [Section 9](#) where applicable.

Outcome	Supports Protocol Objective Number	Subgroups
CR, CRi and CR/CRi response rates by the end of InO treatment	Secondary Objective 2	Overall, and by number of salvage therapies in the pre-index observation period (0,1, ≥ 2).
Number and proportion of patients achieving MRD negativity	Secondary Objective 3	Overall, and by number of completed cycles of InO and by number of salvage therapies in the pre-index observation period (0,1, ≥ 2).
Number and proportion of patients surviving at 3,6 and 12 months after InO initiation	Secondary Objective 4	Overall, and separately in patients with and without follow-up HSCT and by number of salvage therapies in the pre-index observation period (0,1, ≥ 2).

Outcome	Supports Protocol Objective Number	Subgroups
Cause of death	Secondary Objective 4	Overall, and separately in patients with and without follow-up HSCT.
Median OS (95% CI)	Secondary Objective 4	Overall, and separately in patients with and without follow-up HSCT.
Proportion of patients who are relapse free at 3, 6 and 12 months after InO initiation	Secondary Objective 5	All patients, separately in patients with follow-up HSCT.
Median RFS (95% CI)	Secondary Objective 5	All patients, separately in patients with follow-up HSCT.
Proportion of patients initiated on each treatment	Secondary Objective 6	Per treatment (chemotherapy (blinatumomab, other). HSCT, CAR T-cell therapy).
Response to treatment	Secondary Objective 6	Overall, and per treatment (chemotherapy (blinatumomab, other). HSCT, CAR T-cell therapy).
Survival following treatment	Secondary Objective 6	Per treatment (chemotherapy (blinatumomab, other). HSCT, CAR T-cell therapy).
Number and proportion of patients experiencing VOD/SOS during the post-index observation period	Secondary Objective 7	All patients, and in the following subgroups: no HSCT prior to InO, at least 1 HSCT prior to InO, no post-InO HSCT and patients with at least 1 HSCT post-InO. Patients will be assigned to one of these 4 groups which will be analysed separately. For each group, grade of VOD/SOS and follow-up treatment (Follow-up chemotherapy after completion of chemotherapy and follow-up HSCT after HSCT) will be presented.

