The proportion of patients achieving MRD negativity overall and by the number of completed cycles will be presented as a binary variable (see [Section 10.1.4](#)), with the denominator being the total number of patients for whom MRD negativity has been assessed and who have achieved CR/CRi, at any time until the end of treatment with InO (defined as the date of recorded discontinuation of InO). The method of MRD negativity evaluation will be presented as a categorical variable (see [Section 10.1.2](#)). This definition of the MRD denominator supersedes the earlier definition detailed in the protocol and earlier in this SAP.

10.2.5. Secondary Objective 4

To describe OS, and cause of death; in all patients and in patient with or without follow-up HSCT.

The number and proportion of patients surviving at 3, 6 and 12 months after InO initiation will be presented as a categorical variable (see [Section 10.1.2](#)). The median OS and 95% CI will also be presented as Kaplan-Meier plots (see [Section 10.1.5](#)). Cause of death will be presented as a categorical variable (see [Section 10.1.2](#)). A summary table of the number of events and censored patients at each month interval will also be included. OS = death or date patient was last known to be alive – index date. OS will be presented in days or years as appropriate. OS in years will be calculated as the OS in days divided by 365.25. If any components required for the calculation are missing or incomplete for a patient, then that patient will be excluded from the analysis.

10.2.6. Secondary Objective 5

To describe RFS in all patients and in patients with or without follow-up HSCT. Additionally, to describe NRM in patients undergoing follow-up HSCT.

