Distribution of methods used to assess MRD negativity	All patients	Secondary Objective 3	None	Frequency tables and percentages.	Excluded.
Number and proportion of patients surviving at 3,6 and 12 months after InO initiation	All patients	Secondary Objective 4	Overall, and separately in patients with and without follow-up HSCT	Frequency tables and percentages.	Excluded.
Cause of death	All patients	Secondary Objective 4	Overall, and separately in patients with and without follow-up HSCT	Frequency tables and percentages.	Excluded.
Median OS (95% confidence interval)	All patients	Secondary Objective 4	Overall, and separately in patients with and without follow-up HSCT	Kaplan-Meier analysis, median OS measured as being from the date of InO initiation to the date of death. Patients alive at end of follow-up will be censored at date of last visit.	Standard imputation for dates (see Section 7). Otherwise excluded.
Proportion of patients who are relapse free at 3, 6 and 12 months after InO initiation	All patients	Secondary Objective 5	All patients, separately in patients with follow-up HSCT	Frequency tables and percentages.	Excluded.
Median RFS (95% CI)	All patients	Secondary Objective 5	All patients, separately in patients with	Kaplan-Meier analysis, from InO initiation to date of first relapse or date of	Standard imputation for dates (see Section 7).

PFIZER CONFIDENTIAL

Outcome	Analysis Set	Supports Protocol Objective Number	Subgroups	Statistical Method	Missing Data
			follow-up HSCT	last visit before data collection.	Otherwise excluded.
Median NRM (95% CI)	Patients undergoing follow-up HSCT	Secondary Objective 5	None	Kaplan-Meier analysis, from date of follow-up HSCT to date of death or the date of last visit before date of data collection. 95% CI will also be presented.	Standard imputation for dates (see Section 7). Otherwise excluded.
Proportion of patients initiated on each treatment	All patients	Secondary objective 6	Per treatment (chemotherapy (blinatumomab, other). HSCT, CAR T-cell therapy)	Frequency tables and percentages.	Excluded.
Response to treatment	All patients	Secondary objective 6	Per treatment (chemotherapy (blinatumomab, other). HSCT, CAR T-cell therapy)	Frequency tables and percentages.	Excluded.
Survival following treatment	All patients	Secondary objective 6	Per treatment (chemotherapy (blinatumomab, other). HSCT, CAR T-cell therapy)	Frequency tables and percentages.	Excluded.

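### Overall survival starts at the first inotuzumab cycle but is summarised by whether a transplant came later, so the two summaries differ even if transplant has no effect

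*Protocol*

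**What the plan says.** - **Clock.** Protocol 9.2 defines "OS: time from index date to death", and the index date is the start of the first InO cycle. SAP 3.1.1 and 10.2.5 use the same origin. The OS row of SAP 10.2.11 specifies "Kaplan-Meier analysis, median OS measured as being from the date of InO initiation to the date of death".
- **Grouping.** Protocol 9.1 asks for "Median OS (95% CI); overall and in patients with and without HSCT" and for the patients "surviving at 3, 6 and 12 months after InO initiation, and cause of death; overall and in patients with and without HSCT". The OS row of Table 1 in Protocol 9.3 is headed "Summary measures of, in all patients, and separately in patients with and without follow-up HSCT". SAP 7.3 gives the OS subgroups as "Overall, and separately in patients with and without follow-up HSCT".
- **Outputs.** SAP 10.2.5 plans the median with 95% CI, Kaplan-Meier plots and fixed-time survival: "The number and proportion of patients surviving at 3, 6 and 12 months after InO initiation will be presented as a categorical variable".
- **Early deaths.** Protocol 9.2.1 excludes "Patients with <3 months of follow-up since index date, unless death occurs <3 months from index date". Patients who die early therefore stay in the study.
- **What is absent.** The readable text has no landmark, no time-dependent HSCT status and no OS measured from HSCT. Non-relapse mortality (NRM) is the one survival-type endpoint that starts at HSCT (Protocol 9.1, SAP 10.2.6). The limitations in Protocol 9.9 mention neither immortal time nor the HSCT split. The redacted blocks cannot be assessed.

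**The concern.** Group membership depends on something that happens after the clock starts. The time between the first InO cycle and HSCT is free of deaths by construction in the with-HSCT group. The without-HSCT group receives every death that happened before a transplant could take place. This is immortal time, and on its own it always lengthens OS in the with-HSCT group relative to the other.

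Both results belong to a stated secondary objective, in a study whose purpose includes describing effectiveness. A reader who sees the two medians or the two 3-month percentages will tend to read the gap as a benefit of transplant, although the definitions alone can produce it. The confidence intervals do not reveal the problem, because it is systematic and not a matter of sampling error.

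**Working it through.** The documents give no figure for OS by HSCT, so there is none to reproduce. The check asks what the planned summaries would show if HSCT had no effect on survival.

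**Inputs from the documents**
- Median OS on InO: 7.7 months (Protocol 7).
- Share with follow-up HSCT: 77/164 = 47% (Protocol 9.5).
- InO course before HSCT: 2 to 3 cycles of 3 to 4 weeks (Annex 2, List 1). That is 6 to 12 weeks: 42/30.44 = 1.4 months to 84/30.44 = 2.8 months.
- About 25 patients (Protocol 9.5). Subgroups are reported when n > 5 (SAP 7.3).

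**Assumptions**
- Exponential OS.
- HSCT time uniform over the window, with no gap after the last cycle.
- Transplanted patients drawn at random from those alive at the HSCT time.
- No censoring.

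**Closed form for HSCT at a fixed time τ, with share p = 0.47**
- S(t) = exp(−λt), with λ = ln 2 / 7.7 = 0.0900.
- With HSCT: S₁(t) = 1 up to τ, then S(t)/S(τ). The median is τ + 7.7.
- Without HSCT: S₀(t) = [S(t) − p·S₁(t)]/(1 − p).
- τ = 1.4: S(1.4) = 0.882 and S(3) = 0.763. Three-month survival with HSCT is 0.763/0.882 = 0.87; without, (0.763 − 0.47 × 0.866)/0.53 = 0.67. Medians are 9.1 and 6.3 months.
- τ = 2.8: S(2.8) = 0.777. Three-month survival is 0.763/0.777 = 0.98 with HSCT and (0.763 − 0.47 × 0.982)/0.53 = 0.57 without. Medians are 10.5 and 4.4 months.

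**HSCT time spread uniformly over 1.4 to 2.8 months (simulation, 2,000,000 patients)**

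| | With HSCT | Without HSCT | All |
|---|---|---|---|
| Median OS, months | 9.8 | 5.4 | 7.7 |
| Alive at 3 months | 92% | 62% | 76% |
| Alive at 12 months | 41% | 28% | 34% |

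**Range of medians without selection**
- Smallest gap: HSCT at 0.7 to 2.8 months (some after one cycle), 30% transplanted, Weibull shape 1.3: 8.6 against 7.3.
- Largest gap: HSCT at 1.4 to 2.8 months, 60% transplanted, Weibull shape 0.8: 11.2 against 2.0.

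**Would the split be reported?** With 47% transplanted, both groups exceed 5 in 99% of simulated 25-patient studies. In about 84% of those the with-HSCT median is the longer one, where an unbiased comparison would give about 50%.

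**Same data with HSCT as a time-dependent state.** Time before HSCT is counted in the no-HSCT state and time after it in the HSCT state. The ratio of death rates is 1.00, against 0.70 under the fixed split. The false gap disappears.

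**Selection.** A two-stage model used the 5.0-month PFS median in Protocol 7 as a stand-in for RFS, kept OS at 7.7 months, and let 20% of RFS events be deaths. With 30% transplanted, half of them after an RFS event (at 1.4 to 6.8 months), median OS is 7.7 against 7.7. These added inputs are assumptions. They show that selection can cancel the gap.

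**The case against.** The strongest reply is that nothing is being compared. The documents ask for separate summaries. SAP 6.1 states no hypothesis, SAP 6.2 gives no decision rule, and no test, hazard ratio or difference by HSCT is planned. Each summary correctly describes its own subset. All of that stands, and it limits the point to how two descriptive results will be read together. It does not remove the point: both results serve one objective, and no caveat accompanies them. The causal disclaimer in Protocol 9.9 concerns InO and the endpoints, not HSCT.

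Four stronger readings are tempting, and the documents do not support them.
- *The guaranteed survival is at least the full InO course.* A reader might infer this from SAP 10.2.9, which counts transplants after InO is stopped. That section defines the HSCT rate, not the OS groups. Annex 2, Table 4 records whether InO was complete at HSCT, so earlier transplants are allowed for.
- *Nobody can be transplanted before 1.4 months.* That is a modelling assumption. The documents give cycle counts and lengths, not time to HSCT.
- *The observed gap must favour HSCT.* Only the immortal-time part has a fixed direction. Selection can add to it or offset it.
- *RFS is biased in the same direction.* An RFS event can precede HSCT, and HSCT without CR/CRi is itself an RFS event. In the two-stage model the RFS medians are 7.1 against 2.5 months if 47% are transplanted, all while event-free in CR/CRi. They reverse to 4.2 against 5.5 if 30% are transplanted and 40% of transplants follow an RFS event.

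**Conclusion.** The point holds as a misleading pair of descriptive results, not as a wrong estimate or an inflated test. Confidence in the mechanism is high, because it follows from the definitions alone. Confidence in the size is lower: 9.8 against 5.4 months and 92% against 62% at 3 months rest on assumed HSCT timing, an assumed survival shape and no selection. Across the no-selection cases run, the medians go from 8.6 against 7.3 to 11.2 against 2.0 months, and the net gap in real data is uncertain. The primary objective, overall OS and overall RFS are unaffected. The plan should be changed, because the results are a named secondary output and the repair is cheap.

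**What to change.** - In SAP 7.3, 10.2.5 and 10.2.11, keep overall OS from the index date.
- For OS by HSCT, treat HSCT as a time-dependent state, for example with Simon-Makuch curves.
- Also report OS from the date of first follow-up HSCT in transplanted patients, the origin that SAP 10.2.6 already uses for NRM.
- If the index-date split is kept because Protocol 8 states it as an objective, say beside it that the groups are not comparable because of immortal time. Do not set the 3-month proportions against each other.
- Add immortal time and selection for HSCT to the limitations in Protocol 9.9. None of these options removes the selection.
- Give RFS by HSCT the same caution, with its direction stated as uncertain.

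A month-3 landmark is not recommended. If HSCT falls at 2 to 4 months (an assumed window), 48% of transplants come after month 3 and would be classed as no HSCT. Both groups would then exceed 5 in only 55% of 25-patient studies at 47% transplanted.

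**Cost.** SAP wording and short code. HSCT dates are already collected (Protocol 9.3; Annex 2, Table 4), and Protocol 9.7 lets the SAP change non-primary analyses without a protocol amendment. The downside is less familiar plots and few patients at risk late in each state.
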